#### 10.2.1 DOSE REDUCTION FOR SUNITINIB

- Intrapatient dose reduction by 1, and if needed 2- dose level(s) will be allowed (see 6.1) depending on the type and severity of toxicity encountered provided that criteria for patient withdrawal from study treatment have not been met.
- All intra-patient dose reductions are relative to the lowest dose level of the current cycle.
- Recovery to acceptable levels of toxicity must occur within 4 weeks to allow continuation in the study.

[name], Phase II Study of BCG followed by Sunitinib for High risk NMIBC

- No more than 2 dose reductions are permitted in any patient. If further dose reductions are required, patients will discontinue sunitinib therapy. They will continue to be followed per protocol.
- The following table describes the recommended dose modifications for study treatment associated toxicity.

TABLE: DOSE MODIFICATION OF SUNITINIB BASED ON TOXICITY AND GRADE

Recurring grade 3 toxicity requires dose reduction \* Patients who develop grade 3 or 4 hyperlipasemia or hyperamylasemia without clinical or other evidence of pancreatitis, or grade 4 hyperuricemia or grade 3 hypophosphatemia without clinical symptoms may continue study treatment without interruption. \*\*\* Patients with recurrent grade 3 lymphopenia and anemia do not require dose modification. Recurring grade 4 neutropenia or grade  $\geq 3$ thrombocytopenia persisting for at least 5 days requires dose reduction in the next cycle. Grade 4 lymphopenia does not require dose reduction.

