- 3.2.12. Patients with history of or who are suspected to have CHF can be included as long as they are asymptomatic and have an ejection fraction that is equal to or above the institutional lower limit of normal by baseline MUGA (obtained within 28 days of registration or the next business day if falls on a weekend or holiday).
- 3.2.13. QTc interval  $> 500$  msec on baseline EKG (to be done within 6 weeks prior to registration or the next business day if falls on a weekend or holiday).
- 3.2.14. Hypertension that cannot be controlled by medications ( $> 150/100$  mm Hg despite optimal medical therapy).

- 3.2.15. Patient may not have unresolved bacterial infection.
- 3.2.16. Patients with hypothyroidism that cannot be adequately controlled with medication will be excluded. All patients will be monitored at trial initiation with a TSH.
- 3.2.17. Concurrent treatment on another clinical trial. Supportive care trials or non-treatment trials, e.g. QOL, are allowed.
- 3.2.18. Pregnancy or breastfeeding. Female subjects must be surgically sterile or be postmenopausal, or must agree to use effective contraception during the period of therapy. All female subjects with reproductive potential must have a negative pregnancy test (serum or urine) prior to enrollment. Male subjects must be surgically sterile or must agree to use effective contraception during the period of therapy. The definition of effective contraception will be based on the judgment of the principal investigator or a designated associate.
- 3.2.19. Other severe acute or chronic medical or psychiatric condition or laboratory abnormality that may increase the risk associated with study participation or study drug administration, or may interfere with the interpretation of study results, and in the judgment of the investigator would make the subject inappropriate for entry into this study.

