## [name], Phase II Study of BCG followed by Sunitinib for High risk NMIBC

4.2.2 Comprehensive panel: sodium, potassium, chloride, bicarbonate, BUN, creatinine, glucose, calcium, AST, ALT, alkaline phosphatase, bilirubin, total protein and albumin.

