### **Side effects:**

The following side effects, as well as their frequency, have been observed in SUNITINIB clinical studies:

- **Likely (50% or more):** fatigue.
- **Frequent (10-50%):** diarrhea, nausea, upset stomach, taste disturbances, stomatitis/mucositis, vomiting, constipation, yellowing of the skin, anorexia, arthralgia and myalgia, hypertension, dermatitis, headache, blisters and/or rash in hands and feet which may be painful, increased lipase and amylase, hair color changes, shortness of breath, edema, dehydration.
- **Occasional (1-10%):** nosebleeds, leucopenia/neutropenia, anemia, thrombocytopenia, insomnia, cough, fever, increased/more frequent eye tearing, alopecia, increase creatinine, increased LFTs, reduced ejection fraction, increased cardiac enzymes.
- **Rare (less than 1%):** bleeding requiring transfusion (including bleeding into the tumor), thrombosis, infection, hypoadrenalinism, increased TSH, hypothyroidism, decreased blood flow to the brain, pancreatitis, myocardial infarction, bowel perforation/intestinal fistulae, pneumothorax, seizure, temporary loss of vision. One patient developed thrombosis of the portal vein.

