## 13.0 STUDY CALENDAR:

[name], Phase II Study of BCG followed by Sunitinib for High risk NMIBC

		Week 1-6 BCG Course 1		Week 8-12† Sunitinib cycle 1			TURBT or bladder biopsy	Therapeutic Plan			
Required studies	Pre-study	Week1	Week 6	Week 8	Week 10	Week 12	Week 14	1. Residual/Recurrent disease without progression: a. Negative MUGA scan-if positive, proceed to 3. b. 2 nd cycle of BCG followed by sunitinib (as per week 1-14) c. alternative treatment plan per treating clinician 2. No residual disease (Calendar 2): patient will proceed to maintenance BCG therapy per institutional standard a. alternative therapy may be chosen on maintenance at patient/physician discretion 3. Disease progression or patient/clinician desire: proceed to alternative treatment per standard of care			
PHYSICAL											
History and Physical	x			x	x	x					
ECOG performance status	x			x	x	x					
Medication check	x			x	x	x					
Toxicity assessment											
LABORATORY/ STUDIES											
CBCPD	x			x	x	x					
Comprehensive panel	x			x		x					
Magnesium				x		x					
EKG	x										
Dipstick Urine		x	x								
Urine cytology*	x						x				
PT/PTT	x					x					
TSH	x										
MUGA Scan	x										
SPECIMEN SAMPLES											
Urine*		x 	x 	x		x	x				
Bladder biopsy							x				
Serum		x 	x 	x		x					
X-RAYS AND SCANS											
Chest radiograph	x										
CT or MRI abdomen/ pelvis or IVP	x										
Cystoscopy or report confirming eligibility	x										
Drug: Sunitinib				x							
Dispense BP log, Study drug info, and medication diary				x							

\* voided urine cytology obtained in clinic, instrument urine cytology obtained in operating room

† Medical Oncologist will prescribe sunitinib and monitor for toxicity during treatment

 If BCG is given locally no specimens need to be obtained at the Week 1 and Week 6 visits.

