### 16.2 ANALYSES

The primary endpoint for this study will be the complete response rate. This rate will be reported along with 95% confidence intervals.

This study has several secondary endpoints. Response rates at 6 months will be reported with 95% confidence intervals for patients with an intact bladder. Kaplan-Meier estimates will be used to describe recurrence-free survival, including 2-year recurrence-free survival estimates. Toxicity of this therapy will be described, both overall and by grade. Toxicity rates will be tabulated by type and category.

Correlation of changes in VEGF, VEGFR, p53, and other cytokine expression to response will be explored. Markers will be grouped based on terciles of the distribution. Bivariate relationships between the expression level and response status will be assessed with the Mantel-Haenszel chi-square test. Potential analyses will include logistic regression with an outcome of response and Kaplan-Meier methods for time to recurrence. Differences in time to recurrence by expression level will be illustrated by Kaplan-Meier plots and tested using the log-rank test. Due to the sample size and the number of factors we will be statistically testing, these analyses will be considered exploratory until confirmed in a larger, independent, clinical trial.

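### Lipase and amylase have no scheduled test, so a toxicity rate over all treated patients would understate an effect that the protocol itself lists at 10-50%

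*Combined protocol and SAP*

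**What the plan says.** **Dose table footnote (10.2.1).** The exception for "Patients who develop grade 3 or 4 hyperlipasemia or hyperamylasemia without clinical or other evidence of pancreatitis" also names grade 4 uric acid elevation and grade 3 low phosphate when these cause no symptoms. Such patients are allowed to stay on sunitinib without a break.

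**Expected effects (11.2, Side effects).** The list includes "increased lipase and amylase" in the 10-50% group, with no grade given. Raised TSH and hypothyroidism are in the group below 1%. Low phosphate and high uric acid are not listed.

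**Tests (4.2.2 and 13.0).** The panel consists of "sodium, potassium, chloride, bicarbonate, BUN, creatinine, glucose, calcium, AST, ALT, alkaline phosphatase, bilirubin, total protein and albumin". In the calendar, the row "Comprehensive panel" is marked pre-study and at Weeks 8 and 12. Magnesium and PT/PTT, which are outside the panel, have rows of their own. No row exists for lipase, amylase, phosphate or uric acid. TSH is marked pre-study only, in line with 3.2.16: "All patients will be monitored at trial initiation with a TSH". A second course runs "as per week 1-14", with only a MUGA scan added.

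**Analysis (16.2 and 16.4.1).** Toxicity is a secondary objective, to be described overall and by grade: "Toxicity rates will be tabulated by type and category". Every patient is assessable for toxicity from first study treatment.

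**The concern.** A laboratory toxicity can be graded only if someone orders the test. For lipase and amylase the protocol gives a frequent event and a footnote that refers to its grade, but schedules no measurement. A patient with a symptom-free elevation would enter the toxicity table as a non-event, because the denominator is everyone treated and not everyone tested.

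At stake is how the safety result is read. A reader of the final report would take a low or zero count as evidence about sunitinib after BCG, when it would mostly reflect the absence of testing. The footnote is itself about patients without clinical evidence of pancreatitis, and these are the patients least likely to be tested for a clinical reason.

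**Working it through.** **Is there a stated figure to reproduce?** Not for this point, since the plan gives no expected toxicity count. The denominator comes from the two-stage design in 16.1, which I checked by exact binomial: continue if at least 16 of 24 respond, succeed if at least 25 of 36 respond.

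P(success) = Σ over x = 16 to 24 of P(X = x) × P(Y ≥ 25 − x), with X ~ Bin(24, p) and Y ~ Bin(12, p).

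| Quantity | Stated | Recomputed |
|---|---|---|
| False positive error, p = 0.55 | 4.9% | 4.93% |
| Early stop, p = 0.55 | 83% | 82.7% |
| Power, p = 0.75 | 80% | 80.1% |
| Early stop, p = 0.75 | 12% | 12.1% |

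So N = 36 stands (24 if the trial stops at stage 1). In 16.1 these are patients who received sunitinib.

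**Rules and frequencies against tests.**

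| Analyte | Named in 10.2.1 footnote | Frequency in 11.2 | Scheduled test |
|---|---|---|---|
| Lipase, amylase | yes | 10-50%, grade not stated | none |
| Phosphate, uric acid | yes | not given | none |
| TSH | no | below 1% | pre-study only |

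For comparison, the chemistry panel is drawn at Week 8, before sunitinib starts, and at Week 12. Week 12 is therefore its only scheduled on-treatment measurement.

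**Expected lipase/amylase events** = N × rate.
- 36 × 0.10 = 3.6 and 36 × 0.50 = 18
- 24 × 0.10 = 2.4 and 24 × 0.50 = 12

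Scheduled tests would find none of these.

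**Allowing for unscheduled tests.** The documents do not say what share of events such tests would find. I assume 0 to 25%. Expected observed count = 36 × rate × share.

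| Share found (assumed) | True rate 10% | True rate 50% |
|---|---|---|
| 0 | 0 | 0 |
| 5% | 0.18 | 0.9 |
| 10% | 0.36 | 1.8 |
| 25% | 0.9 | 4.5 |
| 100% | 3.6 | 18 |

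At a 25% share, the tabulated rate would be 2.5% where the truth is 10%, and 12.5% where the truth is 50%.

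**How a zero would look.** The exact (Clopper-Pearson) two-sided 95% upper limit for 0/N is 1 − 0.025^(1/N).
- N = 36: 9.7%, just under the 10% floor.
- N = 24: 14.2%, above that floor, so the apparent contradiction arises only at full size.

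With complete testing, a true rate of 10% gives zero in 36 with probability 0.90^36 = 2.3%. If only 10% of events were found, the same true rate gives zero with probability (1 − 0.01)^36 = 69.6%.

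**TSH and hypothyroidism.** Below 1%, fewer than 36 × 0.01 = 0.36 cases are expected, and zero in 36 has probability of at least 0.99^36 = 69.6% even if every patient is tested on treatment.

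**Phosphate and uric acid.** No rate is given, so no expected count can be computed.

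**The case against.** Four points can be made for the plan as it stands.

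1. **Not scheduled does not mean never drawn.** The calendar has a medical oncologist watching for toxicity during sunitinib, with history and physical at Weeks 8, 10 and 12, and nothing forbids extra tests. This stands: symptomatic pancreatitis or hypothyroidism would still be reportable. It does little for symptom-free elevations, which give no reason to test.

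2. **The footnote is permissive.** It lets symptom-free patients with these values continue, and an untested symptom-free patient continues too. This also stands. A reader might infer that missing values would lead to wrong dosing, but for the grades that the footnote names, the documents do not support that. What they show is a mismatch between a grade-based exception and a schedule that collects no grade.

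3. **Five analytes do not make five lost signals.** A reader might infer that the rates for all of them will be near zero by construction. For TSH, the protocol's own frequency makes a near-zero count likely even with testing. For phosphate and uric acid there is no frequency from which to argue.

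4. **The plan promises no lipase or amylase rate.** Section 16.2 names no analyte and does not say that untested patients will be shown as event-free. That is fair, but 16.4.1 makes every treated patient assessable and 16.2 has no rule for untested analytes, so the default table has that effect.

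**Conclusion.** The concern holds for lipase and amylase. They have no scheduled measurement, the protocol lists their elevation at 10-50%, and a rate over all treated patients would be biased low: none of an expected 3.6 to 18 events in 36 would be found by scheduled tests, and 0 to 4.5 would be found if unscheduled tests caught up to a quarter.

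This rests on three assumptions: that the 10-50% from earlier sunitinib studies applies to a single four-week course in this population; that lipase and amylase count as one event, as they are listed; and that unscheduled testing is limited. The 10-50% has no grade attached. The footnote concerns grades 3 and 4, for which the documents give no rate, so the loss in severe events cannot be sized.

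For phosphate, uric acid and TSH the finding is only that on-treatment testing is not scheduled. The primary endpoint, the stopping rule and the sample size are untouched.

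**What to change.** Reconcile 4.2.2, the 10.2.1 footnote, the 11.2 side-effect list and the calendar in 13.0, in one of two ways:

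- **Measure.** Add lipase and amylase to the blood draws already scheduled at Week 8 (pre-sunitinib baseline) and Week 12. The cost is a few assays per patient and no extra visit.
- **Report the limit.** State in 16.2 that these laboratory toxicities were not systematically assessed, give the count together with the number of patients tested, and give no rate over all treated patients. The cost is one sentence.

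The same sentence can cover phosphate, uric acid and on-treatment TSH. How the footnote and the test schedule are brought into line is for the investigators to decide; the statistical requirement is that any tabulated rate uses the patients actually tested as its denominator.

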**Management of cardiac ejection fraction.**

Toxicity	Grade 1	Grade 2	Grade 3	Grade 4
Non-hematologic	Continue at the same dose level	Continue at the same dose level.	Withhold dose until toxicity is grade $\leq 1$ , or has returned to baseline, then resume treatment at the same dose level or reduce the dose by 1 level at the discretion of the investigator*.	Withhold dose until toxicity is grade $\leq 1$ , or has returned to baseline, then reduce the dose by 1 level and resume treatment, or discontinue at the discretion of the investigator*.
cardiac toxicity:	Continue at the same dose level.	Continue at the same dose level except in the event of Non-urgent ventricular paroxysmal dysrhythmia requiring intervention, Withhold dose until toxicity is grade $\leq 1$ , then reduce dose by 1 level and resume treatment.	Remove from further therapy, follow for applicable endpoints	Remove from further therapy, follow for applicable endpoints
Neurotoxicity	Continue at the same dose level.	Withhold dose until toxicity is grade $\leq 1$ , then continue at same dose level.	Withhold dose until toxicity is grade $\leq 1$ , then reduce the dose by 1 level and resume treatment.	Remove from further therapy, follow for applicable endpoints
Fever, chills and "flu-like" symptoms	Continue at same dose level.	Continue at same dose level.	Withhold dose until toxicity is grade $\leq 2$ , or has returned to baseline, then resume treatment at the same dose level.	Withhold dose until toxicity is grade $\leq 2$ , then reduce the dose by 1 level and resume treatment.
Hematologic	Continue at the same dose level.	Continue at the same dose level.	Withhold dose until toxicity is grade $\leq 2$ , or has returned to baseline, then resume treatment at the same dose***.	Withhold dose until toxicity is grade $\leq 2$ , then reduce the dose by 1 level and resume treatment***.

All patients will undergo a MUGA scan prior to enrollment in the study. Patients proceeding to a second cycle of therapy (BCG followed by sunitinib) will undergo a MUGA scan prior to initiation of the second cycle. Patients with an ejection fraction lower than the institutional lower limit of normal will not receive further study treatment per protocol and will be offered alternative therapy as directed by the treating clinician.

## 11.0 PHARMACEUTICAL INFORMATION

### 11.1 TM TICE BCG

#### **Formulation and Packaging**

TICE BCG Live (intravesical) is a freeze-dried preparation made from the Connaught strain of *Bacillus Calmette and Guerin*, which is an attenuated strain of *Mycobacterium bovis* supplied as a vial containing 50 mg of freeze-dried BCG.

#### **Preparation and Dispensing**

The preparation of TICE BCG suspension should be done using aseptic technique. To avoid cross-contamination, parenteral drugs should not be prepared in areas where BCG has been prepared. A separate area for preparation of the TICE suspension is strongly recommended. All equipment, supplies and receptacles in contact with TICE should be handled and disposed of as biohazardous. The individual preparing the TICE should wear gloves, eye protection, and take precautions to avoid contact of BCG with broken skin. If preparation is not performed under a biocontaminant hood, a mask and gown may be worn to avoid inhalation or inadvertent exposure to BCG with broken skin. TICE should not be handled by persons with an immunologic disorder.

Do not remove the rubber stopper from the vial.

(Using Syring Method).

Drawn 1 ml of sterile, preservation-free saline (0.9% Sodium Chloride Injection U.S.P.) at 4-25°C, into a small syringe (e.g., 3 ml) and add to one vial of TICE BCG to resuspend. Gently swirl the vial until a homogenous suspension is obtained. Avoid forceful agitation which may cause clumping of the mycobacteria. Dispense the cludy TICE BCG suspension into the top end of a catheter-tip syringe which contains 49 ml of saline diluent, bringing the total volume to 50 ml. To mix, gently rotate the syringe.

(Using Reconstitutiuon Accessories)

Reconstitutiuon Accessories may be provided with each TICE BCG product order. Refer to the Instructions For Use provided with the accessories for a full description of the product reconstitution procedures using these accessories.

#### **Administration**

## [name], Phase II Study of BCG followed by Sunitinib for High risk NMIBC

A urethral catheter is inserted into the urinary bladder under aseptic conditions, the bladder is drained and then TICE BCG is instilled slowly by gravity, following which the catheter is withdrawn. The patient should lie prone for the 1st 15 minutes and can be up thereafter. At the end of 2 hours, the patient should void seated and should increase fluid intake to flush the bladder.

### **Side effects:**

The following side effects, as well as their frequency, have been observed in BCG clinical studies:

- Likely (50% or more): dysuria.
- Frequent (10-50%): urinary frequency, malaise, hematuria, fever (>38 C), chills, cystitis, urinary urgency, nausea/vomiting, anemia, urinary tract infection
- Occasional (1-10%): bladder cramps/pain, anorexia, renal toxicity, genital pain, arthralgia/myalgia, urinary incontinence, diarrhea, contracted bladder, leukopenia
- Rare (less than 1%): coagulopathy, abdominal pain, liver involvement, systemic infection, pulmonary infection, cardiac (unclassified), headache, skin rash, tissue in urine, constipation, fatigue, local infection, dizziness, thrombocytopenia, ureteral obstruction, and flank pain.

### **Procedure for Handling Drug Spills**

After use, unused product, packaging and all equipment and materials used for instillation of the product (eg, syringes, catheters) should be placed immediately in a container for biohazardous materials and disposed according to local requirements applicable to biohazardous materials. Spills and/or voided urine during the 6 hours following TICE BCG administration should be disinfected with an equal volume of 5% hypochlorite solution (undiluted household bleach) and allowed to stand for 15 minutes before cleaning or flushing toilet.

### **OVERDOSAGE**

Overdosage occurs if more than one vial of TICE BCG is administered per instillation. If overdosage occurs, the patient should be closely monitored for signs of active local or systemic infection. For acute local or systemic reactions suggesting active infection, an infectious disease specialist experienced in BCG complications should be consulted.

### **Drug Storage**

The reconstituted TICE BCG should be kept refrigerated (2-8o C), protected from exposure to direct sunlight, and used within 2 hours. Unused solution should be discarded after 2 hours.

### **Compliance**

Patients will be administered the treatment by a healthcare provider.

#### **11.1.1 AGENT ORDERING**

Commercial supplies of BCG will be used.

## **11.2 PHARMACEUTICAL INFORMATION: SUNITINIB**

### **Formulation and Packaging**

## [name], Phase II Study of BCG followed by Sunitinib for High risk NMIBC

SUNITINIB is a small molecule inhibitor of the receptor tyrosine kinases VEGFR, PDGFR, KIT, and FLT3. SUNITINIB will be supplied as hard gelatin capsules containing 12.5-mg, 25-mg or 50-mg equivalents of SUNITINIB free base.

### **Preparation and Dispensing**

SUNITINIB will be dispensed as capsules at the beginning of each treatment cycle. In case of dose modification, patients will be requested to return all of their previously dispensed medication to the clinic. Capsules will be counted and patients will be dispensed the appropriate number of capsules based on the new dose level.

### **Administration**

Administration will be performed on an outpatient basis. The dose should be taken once daily without regard to meals. Grapefruit and/or grapefruit juice should be avoided during sunitinib administration. The study investigator may implement dose suspension and/or reduction in order to ensure patient safety.

